1.2.3.4 Clinical Activity

Cabozantinib has been studied in a broad selection of tumor types. A summary of the available clinical activity results for cabozantinib in these tumor types is provided in Table 1-5.

Table 1-5: Assessment of Cabozantinib Seen in Multiple Tumor Types

Tumor Type	Study	Median PFS (months)	Week 12 DCR ^a (%)
DTC	XL184-008	not reached	80 ^b
RCC	XL184-008	12.9	72 ^b
Ovarian Cancer	XL184-203 RDT	5.5	50
	XL184-203 NRE	4.0	NA
CRPC	XL184-203 RDT	6.8	66
	XL184-203 NRE	4.6 ^c	NA
	XL184-203 NRE	6.5 ^d	NA
HCC	XL184-203 RDT	5.2	66
Breast Cancer	XL184-203 RDT	4.3	47
Melanoma	XL184-203 RDT	2.8	43
NSCLC	XL184-203 RDT	4.0	38
SCLC	XL184-203 RDT	3.4	43
Pancreatic Cancer	XL184-203 RDT	2.7	35
Gastric/GEJ Cancer	XL184-203 RDT	1.4	33
GB	XL184-201	3.7 ^e	NA

CRPC, castration-resistant prostate cancer; DCR, disease control rate; DTC, differentiated thyroid cancer; GB, glioblastoma; GEJ, gastroesophageal junction; HCC, hepatocellular carcinoma; PFS, progression-free survival; NA, not available; NRE, non-randomized expansion; NSCLC, non-small cell lung cancer; RCC, renal cell carcinoma; RDT, randomized discontinuation trial; SCLC, small-cell lung cancer.

Note: Data reported in this table is from the final endpoint analyses.

^a DCR = (confirmed response [CR] + partial response [PR] + stable disease [1])

^b DCR at Week 17

^c For the CRPC cohort that was assigned a dose of 40 mg qd

[figure not shown]
^d For the CRPC cohort that was assigned a dose of 100 mg qd

^e For Treatment Group C (100 mg qd). See Section 5.5.2.2 for further details.

1.2.3.5 Translational Medicine

Inhibition of the VEGF signaling pathway alone was previously shown to result in more invasive tumors in the transgenic RIP-Tag2 mouse model of neuroendocrine pancreatic cancer that spontaneously develops aggressive tumors (Pàez-Ribes et al. 2009). Treatment with cabozantinib for 3 weeks, from age 14 to 17 weeks, significantly prevented formation of liver metastases (Figure 1-1A) in the RIP-Tag2 model compared with anti-VEGF treatment or vehicle alone. The number of liver metastases was 5-fold greater in anti-VEGF antibody-treated animals compared with vehicle-treated animals, and no liver metastases were detected in cabozantinib-treated animals (Figure 4-1A). In addition, treatment with cabozantinib from age 14 to 20 weeks improved survival (Figure 4-1B). Median survival was 14.7 weeks for vehicle-treated animals (n = 12) and 16.4 weeks for anti-VEGF antibody-treated animals (n = 7; $P < 0.05$ vs vehicle), and all cabozantinib-treated animals survived for the full 20 weeks of observation (n = 6; $P < 0.05$ vs vehicle and anti-VEGF antibody; Figure 1-1B).

Figure 1-1: RIP-Tag2 Model: Survival, Cabozantinib versus Vehicle

11 Final Ver. 25OCT2017
Protocol 17CRC01/EXELIXIS IST56/Version 2.0 10/21/18

One of 7 mice in the cabozantinib group that died from a gavage injury at 3.5 weeks was excluded.

* $P < 0.05$ anti-VEGF antibody vs vehicle

$P < 0.05$ cabozantinib vs anti-VEGF antibody

These results are adapted from Sennino et al. 2012.

These data suggest that dual inhibition of MET and VEGFR2 with cabozantinib leads to potent antitumor efficacy, including protection from metastatic tumor escape, which translates into survival advantages.

1.3 Rationale

1.3.1 Rationale for the Study, Dose, and Schedule

Cabozantinib is a potent, orally bioavailable small-molecule inhibitor of multiple receptor tyrosine kinases which has demonstrated early evidence of activity in a variety of solid tumors. The principal targets of cabozantinib are proteins central to cancer cell growth and tumor angiogenesis: VEGFR2/KDR, MET, RET, and KIT. Cabozantinib is FDA approved for the treatment of progressive metastatic medullary thyroid cancer, where a statistically significant PFS prolongation was demonstrated in the cabozantinib arm compared to placebo [11.2 vs. 4 months; HR 0.28 (95% CI: 0.19, 0.40); $p < 0.0001$]. Cabozantinib also demonstrated a higher response rate as compared to placebo (27% versus 0%; $p < 0.0001$) (Elisei, 2013). Cabozantinib has also been FDA approved for metastatic renal cell carcinoma based on results from the METEOR trial, which showed a significant improvement in median progression free survival with cabozantinib versus everolimus (7.4 months vs 3.8 months, respectively). The rate of progression or death was reduced by 42% with cabozantinib compared to everolimus (HR 0.58; 95% CI, 0.51 to 0.89; $P < 0.001$). The objective response rate was also significantly improved with cabozantinib compared to everolimus (21% vs 5%, respectively; $P < 0.001$).

While mutations in the RET gene underlie much of the efficacy of the drug in medullary thyroid cancer, it is expected that the concurrent inhibition of MET and VEGFR2 may be effective in many solid tumors. In colorectal cancers, MET overexpression was demonstrated in 11/12 human tumor specimens, and demonstrated in vitro that silencing of MET by siRNA led to decreases in colon cancer cell line proliferation, migration, and invasion (Holgren, 2010). In another study of 286 human colorectal cancer specimens, MET overexpression as assessed by immunohistochemistry was seen in 79% (236/286) of specimens. Furthermore, MET overexpression correlated with poor prognosis (De Oliveira, 2009). The proangiogenic ligand, vascular endothelial growth factor (VEGF) binds to at least 3 receptors: VEGFR1 (FLT1), VEGFR2 (KDR), and VEGFR4 (FLT4). The VEGF receptors, VEGFR1 and VEGFR2 (KDR) are expressed on the surface of vascular endothelial cells, and on some bone marrow-derived cells. When activated by ligand binding, VEGF receptors mediate endothelial cell invasion, proliferation, and survival. Clinically, inhibition of VEGF by bevacizumab

in combination with IFL yielded improved progression-free survival and overall survival compared to chemotherapy alone in advanced CRC, demonstrating the potential for antiangiogenic approaches to the treatment of cancer (Hurwitz, 2004). There is evidence that MET and VEGFR pathways cooperate to activate downstream effectors regulating tumor growth (Sulpice, 2009; Gerritsen, 2003). Expression of MET is regulated by the same hypoxia-inducible factor system that governs VEGF expression levels. Therefore, both MET and VEGF are induced in response to tumor hypoxia. The downstream mechanisms involved in MET and VEGFR signaling are complex and may vary depending on context; however, inhibition of these targets with single-agent cabozantinib appears to have the potential to shrink tumors. In xenograft animal studies, treatment with cabozantinib resulted in breakdown of tumor endothelium beginning 24 hours after administration, thus suggesting potent anti-angiogenic effects of cabozantinib. This, in turn, led to significant tumor growth inhibition after cabozantinib treatment in multiple tumor models including human medullary thyroid cancer, human breast cancer, human lung carcinoma, and rat glioblastoma (Yakes, 2011). In CRC patient-derived xenograft models, cabozantinib resulted in significantly decreased growth in all tumors, including regression of 2/12 tumors after 28 days of treatment. Treatment with cabozantinib significantly decreased both the number proliferating cells (KI67 expression) and angiogenesis (CD34 staining) when compared to untreated tumors (Atreya, 2013).

While additional laboratory-based testing will be critical to better understand the mechanism of activity of cabozantinib, human testing in the context of a clinical trial is required to determine its efficacy in an unselected CRC population. Based upon the preclinical evidence above suggesting that MET and the VEGF pathway are promising therapeutic targets in colorectal cancers, as well as the preliminary clinical evidence for both anti-tumor efficacy and safety across a broad range of adenocarcinomas, it is appropriate to proceed with a clinical trial of cabozantinib in patients with advanced colorectal cancers. The experience with VEGF-directed therapy with bevacizumab, aflibercept, and regorafenib in the treatment of advanced CRC highlights the importance of angiogenesis in this disease. In addition, a role for MET signaling in CRC is supported by preclinical and clinical data, and by the potential for the close interplay between MET and VEGFR pathways. Furthermore, it is likely that as-yet unrecognized targets in addition to MET and VEGFR contribute to the broad spectrum of anticancer activity demonstrated in the preclinical models.

2 STUDY OBJECTIVES AND DESIGN

2.1 Study Objectives

The objectives of this study are as follows:

Primary Objective:

- 1) To determine the clinical activity of cabozantinib in patients with refractory metastatic CRC using progression free survival (PFS) as primary endpoint.

Secondary Objectives:

- 1) To determine the response rate (RR) in patients with refractory metastatic CRC treated with cabozantinib.
- 2) To determine the overall survival (OS) in patients with refractory metastatic CRC treated with cabozantinib.
- 3) To describe safety and tolerability of cabozantinib in this group of heavily pretreated patients.
- 4) To retrospectively explore the PFS and RR in patients based on RAS, BRAF, and PIK3CA mutation status.

Exploratory Objectives:

- 1) Exploratory analysis of predictive and pharmacodynamic markers.

2.2 Study Design

2.2.1 Overview of Study Design

This is a Phase 2, single-arm, open-label study of cabozantinib in subjects with metastatic colorectal cancer refractory to standard of care options. The primary endpoint is progression-free survival at 12 weeks. A Simon 2-stage optimal design will be used.

2.3 Treatment Assignment

It is the responsibility of the investigator to assign a subject number before treating each subject with cabozantinib.

2.4 Blinding and randomization

This is an open-label, single-arm study which requires no blinding or randomization.

2.5 Study Sites

This study will be conducted at up to approximately 8 sites.

2.6 Withdrawals

Subjects may discontinue study treatment or withdraw their consent to participate in the study at any time without prejudice. The investigator may withdraw a subject from study treatment or from the study if, in his or her clinical judgment, it is in the best interest of the subject or if the subject cannot comply with the protocol.

In addition, any of the following conditions require discontinuation of the subject from study treatment:

- An AE or intercurrent illness that in the opinion of the investigator warrants the subject's withdrawal from study treatment;
- The investigator believes it is not in the best interest of the subject to continue study
- Specific conditions described in the Management of Adverse Events Sections 3.3.2 and 3.3.2.1;
- Necessity for treatment with other anticancer treatment prohibited by protocol;
- Sexually active subjects who refuse to use medically accepted barrier methods of contraception (eg, male condom, female condom) during the study and for 4 months after discontinuation of study treatment;
- Women who become pregnant or are breastfeeding;
- If the subject does not recover from his or her toxicities to tolerable Grade ≤ 2 within 6 weeks, the subject will have study treatment discontinued unless there is unequivocal evidence that the subject is benefitting. In this situation, a subject may be able to restart therapy with a dose reduction upon resolution of the toxicity and with agreement of the principal investigator / Sponsor;
- Request by regulatory agencies for termination of treatment of an individual subject or all subjects under the protocol;
- Significant noncompliance with the protocol schedule in the opinion of the investigator;
- The minimum dose of study treatment will be 20 mg once daily (qd). Subjects who cannot tolerate 20 mg qd will have study treatment discontinued;
- Progressive disease (PD) or the subject no longer experiences clinical benefit as determined by the investigator

3 TREATMENTS

3.1 Composition, Formulation, and Storage

At study sites, all study medication will be stored as described in the pharmacy manual and inventoried in accordance with applicable state and federal regulations.

3.1.1 Investigational Treatment

Chemical Name: Chemical Name: *N*-{4-[(6,7-dimethoxyquinolin-4-yl)oxy]phenyl}-*N'*-(4-fluorophenyl)cyclopropane-1,1-dicarboxamide, (2*S*)-hydroxybutanedioate

3.1.2 Cabozantinib Tablets

Exelixis internal number: XL184

Cabozantinib tablets are supplied as film coated tablets containing cabozantinib malate equivalent to 20 mg of cabozantinib and contain microcrystalline cellulose, lactose anhydrous, hydroxypropyl cellulose, croscarmellose sodium, colloidal silicon dioxide, magnesium stearate and Opadry® yellow. All tablet strengths are prepared from a common blend and are distinguished by shape. The 20 mg tablets are round and the 60 mg tablets are oval. The components of the tablets are listed in Table 3-1.

Table 3-1: Cabozantinib Tablet Components and Composition

Ingredient	Function	% w/w
Cabozantinib malate (25% drug load as cabozantinib)	Active Ingredient	31.7
Microcrystalline Cellulose (Avicel PH-102)	Filler	38.9
Lactose Anhydrous (60M)	Filler	19.4
Hydroxypropyl Cellulose (EXF)	Binder	3.0
Croscarmellose Sodium (Ac-Di-Sol)	Disintegrant	6.0
Colloidal Silicon Dioxide,	Glidant	0.3
Magnesium Stearate	Lubricant	0.75
Opadry Yellow Film Coating which includes:		
- HPMC 2910/Hypromellose 6 cp		
- Titanium dioxide	Film Coating	4.00
- Triacetin		
- Iron Oxide Yellow		

3.2 Dose, Schedule and Route

Subjects will receive cabozantinib orally at a (starting) dose of 60 mg once daily.

Cabozantinib must be taken on an empty stomach. Subjects must be instructed not to eat for at least 2 hours before and at least 1 hour after taking cabozantinib. Subjects may drink water during this time. Subjects should be instructed to take their cabozantinib dose at approximately the same time every day. If a subject misses a dose, the dose may be taken later only if it is within 12 hours of when the missed dose should have been taken. The missed dose should **not** be made up if it is within 12 hours of the **next** scheduled dose.

Cabozantinib tablets should be swallowed whole with at least 8 ounces of water. The tablets should not be crushed. Grapefruit, grapefruit juice, Seville oranges and their products should be avoided by subjects taking cabozantinib.

In all subjects, dose reductions and delays to manage toxicity are allowed under the guidelines in Section 3.3 below.

3.3 Cabozantinib Dose Modifications, Interruptions, and Discontinuation

Subjects will be monitored for AEs from the time of signing informed consent through their last follow-up visit (30 days after the date of the last dose of cabozantinib treatment.) Subjects will be instructed to notify their physician immediately at the onset of any AE. Causality assessment of AEs will be determined by the investigator. AE severity will be graded by the investigator in accordance with CTCAE v.4.0.

The following should be taken into consideration in decisions regarding dose modifications (reductions or interruption):

- As a general approach, all AEs should be managed with supportive care at the earliest signs of toxicity considered related to the study treatment. Should this be ineffective, dose interruptions and/or reductions should be considered to prevent worsening of toxicity.
- Dose modification criteria for cabozantinib are shown in Table 3-3. Dose interruptions and/or reductions should be implemented for unacceptable toxicity. Doses may be modified at any time while a subject is on treatment.
- The assigned starting dose for cabozantinib is 60 mg/day. Two (2) dose reduction levels of cabozantinib are permitted (see Table 3-2).

- Dose reductions or interruptions may also occur in the setting of lower grade toxicity than defined in Table 3-3, if the investigator feels it is in the interest of a subject's safety and will optimize drug tolerability.
- Interruption of cabozantinib treatment for cabozantinib-related AEs may occur at any time per investigator discretion. If treatment is interrupted due to related AEs for more than 6 weeks, cabozantinib should be discontinued unless there is unequivocal evidence that the subject is benefitting. In this situation, a subject may be able to restart therapy with a dose reduction upon resolution of the toxicity per the discretion of the investigator.
- Dose interruptions for reason(s) other than related AEs (eg, surgical procedures) can be longer than 6 weeks per the discretion of the investigator.

Guidelines for the management of specific AEs are provided in Section 3.3.2.

Table 3-2: Dose Reductions of Cabozantinib

Assigned dose	First Dose Level Reduction	Second Dose Level Reduction
60-mg cabozantinib oral qd	40-mg cabozantinib oral qd	20-mg cabozantinib oral qd

qd, once daily

Cabozantinib should be discontinued if a daily dose of 20-mg cabozantinib (minimum dose) is not tolerated

Table 3-3: Dose Modifications of Cabozantinib for Treatment-Related AEs

CTCAE v.4.0 Grade	Recommended Guidelines for Management^a
Grade 1 AEs	Add supportive care as indicated. Continue cabozantinib treatment at the current dose level if AE is manageable and tolerable.
Grade 2 AEs which are tolerable and are easily managed	Continue cabozantinib treatment at the current dose level with supportive care.
Grade 2 AEs which are intolerable and cannot be adequately managed	At the discretion of the investigator, cabozantinib should be dose reduced or interrupted. Note: It is recommended that dose holds be as brief as possible.
Grade 3 AEs (except clinically non-relevant laboratory abnormalities)	Cabozantinib should be interrupted unless the toxicity can be easily managed with a dose reduction and optimal medical care. Note: It is recommended that dose holds be as brief as possible.
Grade 4 AEs (except clinically non-relevant laboratory abnormalities)	Subjects should have cabozantinib interrupted immediately. Discontinue cabozantinib unless the following criteria are met: 
• Subject is deriving clear clinical benefit as determined by the investigator and agreed by the Sponsor• Toxicity can be managed with a dose reduction following recovery to Grade 1 (or baseline) and optimal medical care

AE, adverse event.

Note: The dose delay and modification criteria for specific medical conditions are provided in Section 3.3.2. For re-treatment criteria of study treatment after a dose hold see Section 3.3.1.1.

^a Study treatment dose adjustment is only needed if the toxicity was deemed related to cabozantinib treatment or had an unclear relationship to cabozantinib treatment.

3.3.1.1 Cabozantinib Dose Reinstitution and Reescalation

If the subject recovers from his or her toxicities to CTCAE v.4.0 Grade \leq 1 or to the baseline value (or lower) and the toxicity was unrelated to study treatment, then study treatment may be restarted with no change in dose.

If the subject recovers from his or her toxicities to Grade \leq 1 or to the baseline value (or lower) the toxicity was deemed possibly related to study treatment, then study treatment may be restarted at a reduced dose (see Table 3-2 for the schedule of dose reductions).

Subjects receiving a daily dose of 20 mg may be restarted at the same dose if deemed safe at the discretion of the investigator. Subjects unable to tolerate a daily dose of 20 mg should discontinue study treatment.

Re-escalation to the previous dose, (but not higher than 60 mg/day) may be allowed at the discretion of the investigator and agreement of the Sponsor for AEs which have resolved or recovered to Grade 1 (or baseline value) and deemed tolerable and easily managed by optimized supportive treatment. Dose re-escalation is not allowed for a drug-related dose reduction triggered by Grade 4 hematologic toxicities or by Grade 4 AEs affecting major organs (eg, central nervous system, cardiac, hepatic, renal).

3.3.2 Warnings and Precautions and Guidelines for the Management of Adverse Events

The most frequent adverse events experienced by \geq 20% of subjects treated with cabozantinib were diarrhea, fatigue, nausea, decreased appetite, vomiting, weight decreased, PPES, constipation, hypertension, dysgeusia, dysphonia, and asthenia.

Adverse events associated with laboratory abnormalities experienced by \geq 5% of subjects treated with cabozantinib include anemia, AST increased, ALT increased, hypothyroidism, hypokalemia, hypomagnesemia, thrombocytopenia, hypocalcemia, hypophosphatemia, lipase increased, lactate dehydrogenase (LDH) increased, neutropenia, ALP increased, hyponatremia, and leukopenia. Mild to moderate QTc interval prolongation (10-15ms) has also been observed with a QT interval calculated by the Fridericia formula (QTcF) not exceeding 500 ms.

Subjects may also experience medically important but less frequent adverse events including arterial and venous thrombotic AEs (eg, DVT, pulmonary embolism [PE], transient ischemic attack [TIA], and myocardial infarction [MI]), severe hemorrhagic events, proteinuria, wound healing

complications, GI perforation, abscesses including intra-abdominal and pelvic abscess, GI and non-GI fistulae formation, osteonecrosis, and reverse posterior leukoencephalopathy syndrome (RPLS).

Cabozantinib treatment should be permanently discontinued for the following adverse events: visceral perforation or fistula formation, severe hemorrhage, serious arterial thromboembolic events, nephrotic syndrome, malignant hypertension, hypertensive emergency, persistent uncontrolled hypertension despite optimal medical management, osteonecrosis of the jaw (ONJ), and RPLS.

Guidelines for the management of AEs (ie, dose interruptions and dose reductions) are presented in the next sections. Each dose reduction of cabozantinib should be to one dose level lower than the current dose. Dose reductions of more than one dose level are acceptable per Investigator judgment. All AEs should also be managed with supportive care at the earliest signs of toxicity. Adverse reactions are presumed to be attributable to study drug. Adverse events classified as “not related” are defined as AEs that are, without question, not associated with the study treatment and attributable to another cause.

The predicted effective plasma half-life of cabozantinib is 55 hours. Thus, when initiating therapy with cabozantinib, it will take most subjects 2 to 3 weeks to reach steady state. If AEs attributable to cabozantinib occur within the initial 3-week period of dosing, early intervention with dose modifications may be justified for AEs that, if worsened, could potentially be dangerous or debilitating, because without a dose adjustment, systemic exposure of cabozantinib might be expected to increase after the onset of the AE.

Events that generally have an early onset include hypocalcemia, hypokalemia, thrombocytopenia, hypertension, PPES, abdominal pain, mucosal inflammation, constipation, diarrhea and vomiting. In addition, earlier onset for events of dehydration was observed in subjects with CRPC when compared with subjects with other tumor types.

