3.3.2.8 Hypertension

Hypertension is a common class effect of drugs that inhibit VEGF pathways and has been reported among subjects treated with cabozantinib.

Treatment guidelines for hypertension deemed related to cabozantinib are presented in Table 3-6. Blood pressure should be monitored in a constant position at each visit (either sitting or supine). In general, subjects with known hypertension should be optimally managed before study entry.

Decisions to decrease or hold the dose of study treatment must be based on blood pressure readings taken by a medical professional and must be confirmed with a second measurement at least 5 minutes after the first measurement. Other than for hypertension requiring immediate therapy, the presence of new or worsened hypertension should be confirmed at a second visit before taking therapeutic action. It is recommended that this second visit occurs within 1 week.

Cabozantinib should be discontinued in subjects with hypertensive crises or hypertensive encephalopathy.

Table 3-6: Management of Hypertension Related to Cabozantinib

Criteria for Dose Modifications	Treatment/Cabozantinib Dose Modification
Subjects NOT receiving optimized anti-hypertensive therapy	
> 150 mm Hg (systolic) ^a and < 160 mm Hg OR > 100 mm Hg (diastolic) and < 110 mm Hg	
 Optimize antihypertensive medications by adding new or additional antihypertensive medications and/or increase dose of existing medications. Reduce study treatment by one dose level if optimal antihypertensive therapy (usually to include 3 agents) does not result in BP <150 mm Hg systolic or <100 mm Hg diastolic If subject is symptomatic interrupt study treatment

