≥ 160 mm Hg (systolic) OR ≥ 110 mm Hg (diastolic)	
 Reduce cabozantinib by one dose level^b or interrupt study treatment per investigator discretion Add new or additional anti-hypertensive medications and/or increase dose of existing medications and monitor subject closely for hypotension. If optimized antihypertensive therapy (usually to include 3 agents) does not result in BP < 150 mm Hg systolic or < 100 mm Hg diastolic, study treatment should be dose reduced further or interrupted Study treatment should be dose interrupted if upper limits of systolic BP (≥ 160 mm Hg) are sustained and not adequately manageable or if systolic BP is > 180 mm Hg or diastolic BP > 110 mm Hg, or if subject is symptomatic Re-start study treatment at the most tolerable dose and re-escalate only if BP falls to and is sustained at < 150 mm Hg systolic and < 100 mm Hg diastolic
Hypertensive emergency ^c	
 Discontinue study treatment

BP, blood pressure.

^a The investigator may decide to initiate or adjust antihypertensive treatment at a lower threshold than systolic BP >150 or diastolic BP >100 based on their clinical judgment and assessment of the individual subject.

^b Permitted dose levels are defined by individual protocols.

^c Hypertensive emergency is defined as uncontrolled elevated blood pressure with clinical evidence of progressive or impending end-organ damage (eg, myocardial infarction/ischemia, intracranial hemorrhage, cerebral ischemia, pulmonary edema,

© 2017 AGICC/Criterion Inc.

PROPRIETARY & CONFIDENTIAL

Template Final Ver. 25OCT2017

Protocol 17CRC01/EXELIXIS IST56/Version 2.0 10/27/18

encephalopathy, kidney damage).

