 - b. Hemoptysis of ≥ 0.5 teaspoon (2.5ml) of red blood within 3 months before the first dose of study treatment;
 - c. Any other signs indicative of pulmonary hemorrhage within 3 months before the first dose of study treatment.
10. The subject has radiographic evidence of cavitating pulmonary lesion(s);
11. The subject has tumor invading or encasing any major blood vessels;
12. The subject has evidence of clinically significant bleeding from tumor invading the GI tract (esophagus, stomach, small or large bowel, rectum or anus), or any evidence of endotracheal or endobronchial tumor within 28 days before the first dose of cabozantinib;
13. The subject has uncontrolled, significant intercurrent or recent illness including, but not limited to, the following conditions:
 - a. Cardiovascular disorders including:
 - i. Congestive heart failure (CHF): New York Heart Association (NYHA) Class III (moderate) or Class IV (severe) at the time of screening;
 - ii. Concurrent uncontrolled hypertension defined as sustained blood pressure (BP) > 150 mm Hg systolic or > 100 mm Hg diastolic despite optimal antihypertensive treatment within 7 days of the first dose of study treatment;
 - iii. Any history of congenital long QT syndrome;

iv. Any of the following within 6 months before the first dose of study treatment:

- unstable angina pectoris;
- clinically-significant cardiac arrhythmias;
- stroke (including transient ischemic attack (TIA), or other ischemic event);
- myocardial infarction;
- thromboembolic event requiring therapeutic anticoagulation (Note: subjects with a venous filter (eg, vena cava filter) are not eligible for this study).

b. GI disorders particularly those associated with a high risk of perforation or fistula formation including:

- i. Active peptic ulcer disease, inflammatory bowel disease (eg, Crohn's disease), diverticulitis, cholecystitis, symptomatic cholangitis or appendicitis, acute pancreatitis or acute obstruction of the pancreatic duct or common bile duct, or gastric outlet obstruction
- ii. Abdominal fistula, GI perforation, bowel obstruction, intra-abdominal abscess within 6 months before randomization,
Note: Complete healing of an intra-abdominal abscess must be confirmed prior to randomization

c. Other clinically significant disorders that would preclude safe study participation;

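### Section 3.3.2 permanently stops cabozantinib for hypertension that stays uncontrolled on optimal therapy, while Table 3-6 reduces, interrupts and restarts; the table's blood pressure target also switches between *or* and *and*.

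*Combined protocol and SAP*

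**What the plan says.** **Stopping rule.** Section 3.3.2 opens a list with "Cabozantinib treatment should be permanently discontinued for the following adverse events". One item on it is "persistent uncontrolled hypertension despite optimal medical management". Malignant hypertension and hypertensive emergency are separate items on the same list. Section 2.6, among the conditions that require a subject to come off treatment, includes "Specific conditions described in the Management of Adverse Events Sections 3.3.2 and 3.3.2.1".

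**Table 3-6, row 1** (systolic above 150 and below 160, or diastolic above 100 and below 110). Antihypertensives are optimized first. Then: "Reduce study treatment by one dose level if optimal antihypertensive therapy", usually three agents, "does not result in BP <150 mm Hg systolic or <100 mm Hg diastolic". Symptomatic subjects are interrupted.

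**Table 3-6, row 2** (systolic at least 160, or diastolic at least 110). The first bullet reduces one level or interrupts, at the investigator's discretion. If optimized therapy misses the same *or* target, "study treatment should be dose reduced further or interrupted". A later bullet interrupts for systolic of at least 160 that is sustained and not adequately manageable, systolic above 180, diastolic above 110, or symptoms. The last bullet begins "Re-start study treatment at the most tolerable dose and re-escalate only if BP falls to and is sustained at" and sets the limits as below 150 systolic *and* below 100 diastolic.

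**Discontinuation in Section 3.3.2.8.** The table discontinues only for hypertensive emergency. The text above it discontinues only for hypertensive crises or encephalopathy.

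**The concern.** An investigator whose patient remains hypertensive on three agents finds two instructions: stop for good (Sections 3.3.2 and 2.6), or reduce or interrupt with a route back to treatment (Table 3-6). The word that might separate them, *persistent*, is not defined and does not appear as a step in the table.

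The second issue concerns the trigger itself. With *or* between the two limits, a patient with one component on target can be read as having met the target, so the dose step is not reached.

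The stakes are patient safety and consistent handling across up to about eight sites. Treatment discontinuations and dose reductions also feed the tolerability results, so sites reading the protocol differently would report different figures for the same clinical course. Section 3.3.2 names hypertension among the events with generally early onset, so the conflict can arise while the 12-week endpoint is still open.

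**Working it through.** The plan states no figure on this point, so there is none to reproduce. The check compares the passages and then tests the logic of the table.

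**Step 1. The two rules side by side**

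| Situation | Sections 3.3.2 and 2.6 | Section 3.3.2.8 and Table 3-6 |
|---|---|---|
| Row 1, optimal therapy misses target | Permanent stop if *persistent* | One-level reduction |
| Row 2, optimized therapy misses target | Permanent stop if *persistent* | Further reduction or interruption |
| Systolic ≥ 160, sustained, not adequately manageable | Permanent stop if *persistent* | Interruption, with a restart bullet |
| Hypertensive emergency | Permanent stop | Discontinue |

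The columns agree only in the last line.

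**Step 2. Do the situations overlap?** The protocol defines uncontrolled hypertension once, in exclusion criterion 13.a.ii: "Concurrent uncontrolled hypertension defined as sustained blood pressure (BP) > 150 mm Hg systolic or > 100 mm Hg diastolic despite optimal antihypertensive treatment". That is an entry criterion, not an on-treatment rule, but it is the only definition available. It describes what the first three lines describe: pressure above 150 or 100 despite optimal treatment. The third line adds that the rise is sustained and unmanageable, which is hard to tell apart from persistent and uncontrolled.

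**Step 3. The and/or logic.** Write S for systolic and D for diastolic.

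- Literal trigger of the two failure-of-therapy bullets: NOT (S < 150 OR D < 100), which equals S ≥ 150 AND D ≥ 100.
- Alternative reading, failing either target: S ≥ 150 OR D ≥ 100.
- Restart bullet target: S < 150 AND D < 100.

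| S/D | Row entered | Literal trigger | Alternative trigger | What else acts |
|---|---|---|---|---|
| 155/90 | 1 | No | Yes | Antihypertensives optimized; interrupted if symptomatic |
| 140/105 | 1 | No | Yes | As above |
| 155/105 | 1 | Yes | Yes | As above |
| 165/90 | 2 | No | Yes | First bullet: reduce or interrupt |
| 140/112 | 2 | No | Yes | Interrupt (diastolic above 110) |
| 185/95 | 2 | No | Yes | Interrupt (systolic above 180) |

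At 155/90 the patient has literally met the target in the trigger bullet and missed it in the restart bullet.

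**Step 4. How wide is the gap?** Take every whole-number pair with S from 90 to 220 and D from 50 to 130.

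- Exactly one component at or above 150/100: 71 × 50 + 60 × 31 = 3550 + 1860 = 5410 pairs. The literal trigger fires for 0 of them and the alternative for all 5410.
- Of these, pairs that enter row 2, where the first bullet already reduces or interrupts: 61 × 50 + 60 × 21 = 3050 + 1260 = 4310.
- Of these, pairs that meet S > 180 or D > 110 and are interrupted: 40 × 50 + 60 × 20 = 2000 + 1200 = 3200.

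These counts describe the wording and are not patient frequencies. The literal gap is therefore limited to two steps: the row 1 dose reduction, for an asymptomatic isolated systolic of 151–159 or diastolic of 101–109, and the row 2 further reduction or interruption. An example of the second is a patient who enters at 165/90, is reduced one level, and settles at 155/90 on three agents.

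**Step 5. Patients affected.** The documents do not say how many patients stay uncontrolled on optimized therapy. For background only, Table 1-3 gives hypertension in 29.4% and Grade 3 or higher in 13.7% (330/2410). Applied to 44 patients, 0.294 × 44 = 12.9 and 0.137 × 44 = 6.0. Neither is a count of refractory cases, and the pooled studies include 140 mg capsule dosing, whereas this trial starts at 60 mg.

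**The case against.** **A staged reading is available.** Table 3-6 sits under a heading for subjects not yet on optimized therapy, and Section 3.3.2 introduces the later sections as guidance on interruptions and reductions. On this view the table is the ladder and permanent discontinuation is its end, reached when hypertension persists after every step. The protocol also has general end points: discontinuation if 20 mg is not tolerated, and after more than six weeks' interruption for related events unless benefit is unequivocal.

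This is plausible, but no passage states it. The bullets under that heading go on to cover failure after optimization, the table has no row or time limit for *persistent*, and the six-week rule has its own route back to treatment. Nor can careful alignment of the 3.3.2 list be presumed: it also requires permanent discontinuation for osteonecrosis of the jaw, which Section 3.3.2.16 lets a subject restart after once healed and with sponsor approval.

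**The *or* can be read as failing either target.** Both rows are entered on a single component, and the restart bullet uses *and*. Section 3.3 also lets investigators reduce or interrupt at their discretion. This stands: the wording is ambiguous, not a certain failure to act. A dose-modification trigger should still not need interpretation.

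**Stronger readings a reader might infer.**

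- That the table never acts on an isolated rise. It does, through the other row 2 bullets and for symptomatic subjects, and even 155/90 calls for antihypertensives to be optimized.
- That the row 2 bullets contradict each other above 110 diastolic. They do not: the later bullet narrows the choice given in the first, and interrupting satisfies both.
- That stopping treatment ends tumour scanning. Table 5-1 marks no post-treatment scan, but Section 5.5 sets the six-weekly schedule without an on-treatment condition and Section 5.3 continues disease-status follow-up, so the documents do not settle it.

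**Conclusion.** The stopping instruction is inconsistent as written. For hypertension not controlled on optimized therapy, Sections 3.3.2 and 2.6 point to permanent discontinuation and Table 3-6 to reduction, interruption and restart, with no stated point of transfer. This conclusion rests on the text and on reading *uncontrolled* as exclusion 13.a.ii defines it.

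The and/or mismatch is the lesser part. It leaves a literal gap in two steps of Table 3-6, for a rise in one component only, and a reasonable reader could close it by interpretation.

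The effect on patients cannot be sized from the documents. No sample size, error rate or decision cut-off is altered. The consequence lies in safety, consistency across sites and the tolerability summaries.

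**What to change.** Reconcile Sections 2.6, 3.3.2 and 3.3.2.8 (text and Table 3-6) so that one stated sequence applies to hypertension uncontrolled on optimized therapy. The sequence should say where reduction and interruption end and where, if anywhere, permanent discontinuation begins, and it should define *persistent* in the table if the term is kept. Make the and/or logic of the blood pressure target the same in the row 1 and row 2 failure-of-therapy bullets and the restart bullet, so that a rise in one component has a single stated handling. Which action and which thresholds apply is for the sponsor's clinicians to decide.

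The cost is a few lines in one table and a sentence or two of text, in an amendment that goes through the review described in Section 13. No visits, data items or analyses are added.
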